#### 4.3 **Stratification for Treatment**

Stratification for treatment of ependymoma will be determined when radiation therapy planning is initiated. There is no limit to the number of participants in each stratum.

Stratum 1 (initial pattern of failure is local); disease confined to primary site; age >12 months at time of enrollment to < 21 years. Treatment: focal irradiation.

Stratum 2 (initial pattern of failure is metastatic); neuraxis metastatic disease without equivocal evidence of local failure; age > 36 months at time of enrollment to < 21 years. Treatment: craniospinal irradiation.

Stratum 3 (initial pattern of failure is both local and metastatic): neuraxis metastatic disease with unequivocal evidence of local failure; age > 36 months at time of enrollment to < 21 years. Treatment: craniospinal irradiation.

Stratum 4 (initial pattern of failure is local): disease confined to primary site; age >36 months at time of enrollment to < 21 years; tumor shows presence of 1q gain. Treatment: craniospinal irradiation (optional).

#### 4.4 **Radiation Therapy**

Radiation therapy will be started once a final treatment plan has been developed and approved. There is no time limit for the interval from enrollment to when irradiation commences

#### 4.5 Chemotherapy

Rev. 3.2 dated: 1/19/2023

The use of chemotherapy prior to or after re-irradiation will be allowed for patients enrolled on this study. The use of chemotherapy during the initial management of ependymoma has become more commonplace as investigators seek to determine the role of chemotherapy for patients with initially unresectable ependymoma [213] or in patients after gross-total resection [214]. The impact of chemotherapy on disease control and complications will be considered in the statistical design. It is envision that as combined modality therapy becomes more common for children, with ependymoma, the novel agents [215] tested in conjunction with re-irradiation will vary over time and according to specific clinical and biological parameters.

> St. Jude Children's Research Hospital IRB Approval date:

IRB NUMBER: Pro00004349

#### 5.0 RADIATION THERAPY GUIDELINES

#### **5.1** General Guidelines

Radiation therapy on this protocol will be based on extent of disease, extent of resection and location. The allowed treatment modalities include conformal or intensity-modulated radiation therapy using photons or proton therapy using all available methods.

# 5.2 Treatment Planning and Specifics

The guidelines for this study were based on the experience treating patients with ependymoma at St. Jude Children's Research Hospital. This includes patients treated with radiation therapy at the time of initial diagnosis as well as recurrence after prior focal irradiation. Patients with local failure will be treated with surgery and a second course of focal irradiation. The total dose for the second course of irradiation for most cases will be 54Gy. The total dose may be attenuated for patients with prior history of significant treatment-related complications or in the setting of significant dose heterogeneity or high-dose treatment volumes. Patients with metastatic failure will be treated with metastasectomy and craniospinal irradiation. Craniospinal irradiation (36-39.6Gy) will include focal boost treatment of primary and metastatic sites (50.4-59.4Gy) depending on location, extent of resection and target volume. Patients with combined local failure will undergo metastasectomy, primary site resection and craniospinal irradiation.

Targeting the primary site for retreatment follows the principle of minimizing dose to normal tissue, irradiating only the site of known recurrent disease and not irradiating the entirely of the tumor bed at the time of initial diagnosis. It is anticipated that some tissues will receive a combined dose  $59.4 \text{Gy} + 54 \text{Gy} \sim 114 \text{Gy}$  from the first and second courses of irradiation, respectively.

The prescribed dose for ependymoma has evolved to a standard of 59.4Gy when using a clinical target volume margin of 1cm for all children except those under the age of 18 months treated with gross-total resection. There are ample data demonstrating that these prescribed doses and target volumes are reasonable and safe. In the setting of recurrent disease and prior irradiation, the dose of 59.4Gy is appropriate for previously untreated brain and the limit for previously irradiated tissue will be 54Gy. The neuraxis dose for metastatic ependymoma has been chosen to achieve the highest level of disease control; however, there may be instances when portions of the neuraxis will receive less than 36Gy owing to concerns about potential risks.

IRB Approval date:

Rev. 3.2 dated: 1/19/2023 Protocol document date: 1/19/2023 St. Jude Children's Research Hospital

IRB NUMBER: Pro00004349

The CSI component of treatment is planned and administered in a relatively conventional manner; however, limited volume irradiation of the primary site or metastatic sites after CSI is amenable to a spectrum of conformal planning and delivery techniques. The guidelines for this study are generalized to provide consistency in the targeting, dosimetry and reporting.

Investigator discretion will be used in various minor aspects of treatment including the total dose prescribed to the previously irradiated cervical spinal cord and brainstem, the total neuraxis dose, total spinal and intracranial dose for metastatic sites, and total primary site dose.

# 5.3 Indications for Radiation Therapy

Patients enrolled on this protocol will receive radiation therapy after documented evidence of tumor progression or recurrence. In most cases, surgery will be performed for diagnostic and therapeutic purposes prior to irradiation. The goal of surgery is to achieve gross total resection of all imaging visible residual tumor.

#### 5.4 Timing

The general goal is to initiate radiation therapy within 12 weeks of last surgery performed at the time of recurrence; however, there is no required time interval from the time of surgery to the initiation of radiation therapy.

There are no contraindications to radiation therapy; however, patients taking phenytoin should be weaned and/or switched to a different anticonvulsant as soon as possible.

#### 5.5 Emergency Irradiation

Urgent irradiation is not envisioned under any circumstance.

Equipment and Methods of Delivery and Verification: all photon and proton therapy modalities will be allowed on this protocol including all energy of photon and proton beams. Photon treatment may be indicated when proton systems are not available.

#### 5.6 Treatment Planning

CT (volumetric) based planning is required to optimize dose to the neuraxis or target volume(s) while protecting normal tissues. Organs at risk within the irradiated volume should be contoured including those required. A dose-volume histogram (DVH) is necessary to determine target coverage and evaluate dose to normal tissues. CT section thickness should be < 2-3mm when planning for treatment of focal targets in the brain and < 5mm for craniospinal irradiation.

#### 5.6.1 Treatment Planning

al date: St. Jude Children's Research Hospital IRB NUMBER: Pro00004349

CT (volumetric) based planning is required to optimize dose to the target while protecting normal tissues. Organs at risk within and external to the irradiated volume should be contoured. A DVH is necessary to assess target coverage and evaluate dose to normal tissues. Three-dimensional imaging data will be the basis for treatment planning and will be used to define target volumes and organs at risk. The size, shape and location of the target volume and its relationship to the surrounding anatomy will be incorporated into the decision regarding the use of the specific planning method and the goals of treatment which include target volume coverage, normal tissue sparing, feasibility of delivery and the potential for verification. Target coverage and dose to critical structures will be evaluated by examining isodose distributions and dose-volume histograms for the target volumes and normal tissue structures. Based on these evaluations, the optimal plan that maximizes conformity of treatment and minimizes dose to normal tissues will be selected. The homogeneity of dose will be optimized across the targeted volumes.

#### 5.6.2 CT Data

At the outset of this protocol, CT data will be obtained in the treatment position as the fundamental data set to which MR data will be registered for treatment planning and measurements of brain shift, target volume change and patient's positioning. The fundamental data set will include the volume from the vertex to the base of the skull and will hopefully encompass all tissues down to the level of the sternal notch. Each slice thickness will be approximately < 2mm throughout the volume. Intravenous contrast may be used unless it is contraindicated or deemed unnecessary by the treating radiation oncologist. The use of proton therapy necessitates a non-contrast CT in addition to a contrast-enhanced CT when acquired.

#### **5.6.3** MR Data

MR data will be registered to CT data for planning and evaluation. MR data includes imaging obtained pre and post-operatively and studies performed as part of the planning process. Diagnostic imaging MR data (DIMR) will include 2-and/or 3-dimensionally acquired T1-weighted pre- and post-contrast imaging, T2-weighted imaging and post-contrast FLAIR sequences to identify tumor. Radiation oncology MR data (ROMR) will include imaging studies performed for planning purposes and during treatment to monitor for changes in target and normal tissue volumes and patient positioning.

#### 5.6.4 Immobilization and Simulation

Patients will be immobilized according to their level of cooperation, clinical condition and the suitability of available devices relative to their tumor location and the goals of treatment. Daily general anesthesia will be used when required to achieve satisfactory immobilization and localization. At the outset of this

IRB Approval date:

Rev. 3.2 dated: 1/19/2023 Protocol document date: 1/19/2023 St. Jude Children's Research Hospital

IRB NUMBER: Pro00004349

protocol, supine-position immobilization devices will be used. Fiducial markers may be placed prior to therapy when requested.

#### **5.6.5** Verification Simulation

After treatment planning, the patient may need to be repositioned at the treatment isocenter (as defined by the treatment plan) for verification. This may take place in the simulator (CT or MR) or using the verification imaging systems associated with the treatment device.

#### **5.6.6** Verification of Spatial Positioning

Portal and volumetric mV or kV imaging are interchangeably used to verify patient position.

#### 5.7 Target Volumes

General Comments International Commission on Radiation Units and Measurements (ICRU) [216-218] Reports 50, 62 and 78 define prescription methods and nomenclature that will be utilized for this study. Although the MRI obtained immediately prior to radiation therapy should be used for treatment planning, the target volumes for this study will be determined by the collective information that delineates the extent of disease before and after surgical resection of recurrent tumor. Most patients with ependymoma require a combination of preand post-operative MR sequences to delineate the extent of disease. MR pre- and post-gadolinium contrast T1, T2, and FLAIR sequences should be reviewed. The sequence that best defines the extent of residual disease and post-operative tumor bed should be used to determine the GTV and registered to the treatment planning CT. Registration of the PET studies may also be useful. The GTV, CTV and PTV and normal tissues must be outlined on all axial imaging slices on which the structures are visible.

#### 5.7.1 Targeting for patients with local recurrence

**Primary Site Irradiation** 

The patient with recurrent disease at the primary site and no evidence of metastasis will receive focal irradiation of the primary site using the targeting guidelines provided below. Exceptions will include patients with tumors demonstrating the presence of 1q gain at any point in their treatment history. They will be given the option of craniospinal irradiation and will follow targeting guidelines similar to those who have metastatic disease.

#### 5.7.2 Targeting for patients with metastatic disease

IRB Approval date: St. Jude Children's Research Hospital IRB NUMBER: Pro00004349

Craniospinal Irradiation (CSI): The CSI volume includes the entire subarachnoid volume with special attention to identification and inclusion of the cribriform plate and temporal fossae intracranially; the full width of the spinal subarachnoid space intraspinally and the inferior aspect of the thecal sac. CSI will be reserved for patients with evidence of neuraxis dissemination based on evaluation of CSF cytology or imaging of the brain and spine and will be given according to the guidelines provided below.

Primary Site Irradiation: Patients with metastatic disease may also have evidence of primary site failure and will receive supplemental irradiation to the primary site immediately following craniospinal irradiation. Targeting guidelines for the treatment of the primary site in this setting will follow the guidelines used for primary site irradiation in the absence of metastatic disease.

Metastatic Site Irradiation: Treatment of metastatic disease requires investigator discretion. All resected lesions and overt metastatic disease >0.3cm in maximal thickness should receive supplemental irradiation in addition to CSI when practical. Smaller lesions may also be treated at the discretion of the treating physician. This will include lesions in the brain and spine and using the guidelines outlined below.

#### 5.8 Definitions for GTV, CTV and PTV

#### 5.8.1 Gross Tumor Volume

Rev. 3.2 dated: 1/19/2023

Gross tumor volume (GTV) is based on the post-operative MR examination and includes gross residual tumor and the tumor bed at the primary site. In defining the GTV, the investigator should consider the pre-operative imaging examination that defined the extent of recurrent tumor and the tissues involved anatomically. The GTV in most cases will be a contracted or collapsed tumor bed. Tissue defects resulting from surgical approaches will not be included as part of the GTV when not previously involved by tumor. Investigators should register the pre-operative MR imaging sequence that demonstrated tumor and contour the structure to be identified as GTV\_PREOP to assist in the delineation and evaluation of the GTV. In the setting of gross-total resection, the post-contrast T1-weighted MR sequence is generally the most useful. In the setting of non-enhancing residual disease, T2-weighted imaging may be required. The GTV will take into account changes in brain anatomy resulting from tumor resection or CSF shunting.

- GTV is the volume of tissue containing the highest concentration of tumor cells.
- GTV includes the post-operative tumor bed which is the edge of the resection cavity.
- GTV includes residual disease defined by post-operative neuroimaging.

IRB Approval date: St. Jude Children's Research Hospital

IRB NUMBER: Pro00004349

- The surgical corridor should not be included in the delineation of the GTV unless suspected to contain tumor.
- When there is discrepancy between imaging studies or intra-operative findings, the larger volume will define GTV.

#### **5.8.2** Clinical Target Volume

Clinical target volume (CTV) includes the GTV with an added margin that is meant to treat subclinical microscopic disease and is anatomically confined (i.e., the CTV is limited to the confines of the bony anatomy, dura, falx and tentorium where applicable or extends up to but not beyond neuroanatomic structures through which tumor extension or invasion is certain not to have occurred); the CTV margin should not exceed 0.5cm and should generally include 0.3cm of normal tissue. When the GTV approaches the boundary of an anatomic compartment, the CTV will extend up to and include the boundary. The CTV margin chosen for this study requires treatment planning MR and/or diagnostic MR imaging data with image section thickness  $\leq$  0.5cm.

- CTV is defined as the volume of tissue containing subclinical microscopic disease
- CTV for this protocol is the GTV with an anatomically confined margin of ≤ 0.5cm
- CTV should be tailored at tissue interfaces where invasion/infiltration is not likely
- CTV may be manually moved inward to the inner-table of the bony calvarium
- CTV may be limited to the brainstem surface which is ≤ 0.2-0.3cm depth of the brainstem contour.

#### **5.8.3** Planning Target Volume

Rev. 3.2 dated: 1/19/2023

Planning target volume (PTV) is a concept associated with photon therapy includes a margin which is added to the CTV in 3-dimensions to create the PTV. It is geometric and not anatomically defined. The PTV has two components, the internal margin (IM) and the set-up margin (SM). The IM is meant to compensate for all movements and variations in size and shape of the tissues contained within the CTV. The SM is meant to account for set-up, mechanical and dosimetric uncertainties related to daily patient positioning, treatment equipment and software. For this study, the PTV margin should be 0.2-0.3cm. The use of a PTV margin of 0.2-0.3cm requires image-guided radiation therapy methods are used on a daily basis or alternatively a fixation system or verification system with similar performance. Given that the CTV is generally confined to the intracranial space, the PTV may extend into or beyond bone but is unlikely to extend beyond the surface of the patient. The PTV margin chosen by the treating investigator requires treatment planning MR and/or diagnostic MR imaging data with imaging section thickness ≤ the chosen PTV margin. In summary, the PTV will include the

IRB Approval date: St. Jude Children's Research Hospital

IRB NUMBER: Pro00004349

CTV plus a geometric margin of 0.2-0.3cm in all dimensions. The PTV may extend beyond bone margins and the skin surface.

Craniospinal Irradiation (CSI): The CSI volume includes the entire subarachnoid volume with special attention to identification and inclusion of the cribriform plate and temporal fossae; the full width of the spinal subarachnoid space and the inferior aspect of the thecal sac.

Craniospinal Irradiation-CT Planning: CT studies obtained uniquely for the CSI planning process are allowed and may also serve as the basis for planning boost treatment. CT studies will be performed whenever possible and the information used for craniocaudal intensity modulation. For the cranial component of treatment, the external contours of the skull and neck are viewed in the AP direction and points are chosen to divide the cranial field into 2-4 fields to achieve a field-within-a-field plan and lateral homogeneity over the craniocervical junction. For the spinal component of treatment, the spinal cord and canal are contoured and viewed laterally and points are chosen to divide the spinal field into 4-6 fields to achieve field-within-a-field plan and antero-posterior homogeneity over the spinal cord and thecal sac. The following parameters are suggested: volume - cranial vertex to perineum; section thickness < 5mm; image matrix - 512². The administration of IV contrast is not required.

Patients may have one or more metastatic lesions. These lesions may or may not be surgically removed. The nomenclature for the targeted volumes will follow those used for primary site irradiation with additional descriptors mean to assist in the evaluation of the case after the completion of treatment. For example, MGTV1\_intracranial or MGTV1\_right\_lateral ventricle and subsequent modifications for CTV and PTV will be helpful.

Relevant to proton therapy, the PTV may be used to select the appropriate beam size and beam arrangements to achieve lateral coverage of the targeted volume and to minimize heterogeneity. The PTV will not be used to determine the distal range for the individual proton beams but will be used to report dose according to ICRU Report-78. The proton distal target margin will be determined per beam using the guidelines noted in this protocol.

#### 5.9 Target Dose

Rev. 3.2 dated: 1/19/2023

#### 5.9.1 Dose Definition

Photon dose is to be specified in centigray (cGy)-to-muscle. For proton therapy, the absorbed dose is specified in CGE, which is the same as ICRU 78 DRBE [218] using a standard RBE of 1.10 with respect to water. The units of Gy and CGE will be interchangeable with reference to prescription dose, normal tissue constraints, etc.

#### 5.9.2 Prescribed dose and fractionation

IRB Approval date: St. Jude Children's Research Hospital IRB NUMBER: Pro00004349

The patient should be treated with one fraction per day. All fields should be treated each day in photon treatments. Simultaneous integrated boost is not allowed.

Table Prescribed Doses and Fractionation

Total Dose by Site	Target Volume	Dose/fraction	Number of Fractions
Neuraxis 3600-3960CcGE/cGy	CTV CSI /PTV CSI	180CcGE/cGy	20-22
Primary Site 5040-5400cGy	CTV PS /PTV PS	180CcGE/cGy	10-30
Metastases 5040-5940cGy	CTV X /PTV X	180CcGE/cGy	5-13

The total dose to the target volume CTV (proton) or PTV (photon) prescription isodose surface will be 5400CcGE/cGy administered in 30 fractions of 180CcGE/cGy. The patient should be treated with one fraction per day. All fields should be treated each day in photon treatments. Exceptions will include unanticipated changes in patient's clinical condition, logistical considerations owing to holidays, weather, equipment failure and the need to complete the course of treatment in the least number of elapsed days. Two treatments in one calendar day will be discouraged. We will consider a single fraction reduction in the dose regimen for cases where significant dose heterogeneity are encountered. Investigator discretion may be used to alter the dose per fraction 150-200CcGE/cGy per day when indicated and requires PI approval. The total dose may be attenuated - 3420CcGE/cGy instead of 3600CcGE/cGy CSI or 5040CcGE/cGy instead of 5400CcGE/cGy primary site - for patients with prior history of significant treatment-related complications or in the setting of significant dose heterogeneity or high-dose treatment volumes. We will also consider alterating the craniospinal dose when there are concerns about excessive risks regarding treatment-related complications,

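### In the Section 5.9.2 prescription table, some fraction counts do not fit the stated total doses at 180 cGy, and boost counts are not labelled as boosts

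*Combined protocol and SAP*

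**What the plan says.** The table in Section 5.9.2 has one row per site, all at 180 cGy per fraction:

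- "Neuraxis 3600-3960CcGE/cGy", 20 to 22 fractions;
- "Primary Site 5040-5400cGy", 10 to 30 fractions;
- "Metastases 5040-5940cGy", 5 to 13 fractions.

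The first column is headed as a total dose. Nothing in the table says whether a count is a whole course or a boost. The text below it prescribes "5400CcGE/cGy administered in 30 fractions of 180CcGE/cGy" without restricting this to focal treatment.

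The same section allows departures: "Investigator discretion may be used to alter the dose per fraction 150-200CcGE/cGy per day when indicated and requires PI approval"; "We will consider a single fraction reduction in the dose regimen for cases where significant dose heterogeneity are encountered"; and attenuated totals of 34.2 Gy for the neuraxis and 50.4 Gy for the primary site.

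Section 5.7.2 makes metastatic-site treatment, and primary-site treatment in patients with metastatic disease, additional to craniospinal irradiation. Section 5.9.5 says the craniospinal part generally comes first and the boost follows.

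Section 5.2 gives one range for "focal boost treatment of primary and metastatic sites (50.4-59.4Gy", which varies with the site, the resection and the target volume. It also says that "the limit for previously irradiated tissue will be 54Gy".

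**The concern.** Total dose, dose per fraction and number of fractions are tied together by multiplication, so any two fix the third. Where the printed counts do not fit the printed totals, a course can satisfy one column and fail the other.

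This table is the operative prescription for the trial's intervention. Dose bears on both progression-free survival, part of the primary objective, and central nervous system necrosis, which has its own stopping rule in Section 11.1. Section 10.2 includes treatment in compliance monitoring. A monitor asked whether 10 primary-site boost fractions after 39.6 Gy comply would get a yes from the fraction column and a no from the dose column. Section 11.1 also records that a collaborating site was added, and such a site may not share the lead centre's unwritten conventions.

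**Working it through.** **Inputs** (Section 5.9.2): 1.8 Gy per fraction; craniospinal dose C of 36 to 39.6 Gy, or 34.2 Gy if attenuated; primary-site total 50.4 to 54 Gy; metastasis total 50.4 to 59.4 Gy.

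**Formula:** fractions needed = (T − C) / 1.8, where T is the cumulative dose at the site and C = 0 for focal treatment alone.

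**1. Neuraxis row.** 20 × 1.8 = 36.0 Gy and 22 × 1.8 = 39.6 Gy. The row reproduces exactly.

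**2. Other rows read as stand-alone courses.** Metastases: 5 × 1.8 = 9.0 Gy and 13 × 1.8 = 23.4 Gy. Primary site: 10 × 1.8 = 18.0 Gy and 30 × 1.8 = 54.0 Gy. Only the 30 works as a whole course. The smaller counts make sense only as boosts, as Sections 5.7.2 and 5.9.5 imply.

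**3. Fractions needed, by craniospinal dose.**

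| Craniospinal dose | to 50.4 Gy | to 54 Gy | to 59.4 Gy |
|---|---|---|---|
| none (focal) | 28 | 30 | 33 |
| 34.2 Gy (attenuated) | 9 | 11 | 14 |
| 36 Gy | 8 | 10 | 13 |
| 39.6 Gy | 6 | 8 | 11 |

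The first two columns of counts bound the primary site; the first and third bound metastases.

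**4. Metastases, lower count of 5.**
- 34.2 + 5 × 1.8 = 43.2 Gy
- 36 + 5 × 1.8 = 45.0 Gy
- 39.6 + 5 × 1.8 = 48.6 Gy

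All are below 50.4 Gy. At the largest permitted fraction, 39.6 + 5 × 2.0 = 49.6 Gy, still below. Reaching 50.4 Gy in five would need (50.4 − 39.6) / 5 = 2.16 Gy per fraction, outside the permitted 1.5 to 2.0 Gy. The smallest count that arithmetically reaches 50.4 Gy at 1.8 Gy is 6, after 39.6 Gy.

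**5. Primary site, 10 to 30.**
- Consistent: 36 + 10 × 1.8 = 54.0 Gy, and 30 × 1.8 = 54.0 Gy focally.
- Omitted after 39.6 Gy: 6, 7 and 8 fractions (50.4, 52.2 and 54.0 Gy), which are all the counts that fit. The printed minimum gives 39.6 + 10 × 1.8 = 57.6 Gy. Even at 1.5 Gy per fraction it gives 39.6 + 15 = 54.6 Gy, above 54.
- Omitted after 36 Gy: 8 and 9 fractions (50.4 and 52.2 Gy).
- Included without fitting: 11 to 27. Eleven after 36 Gy is 55.8 Gy, above 54; 27 focally is 48.6 Gy, below 50.4. Eleven does fit after the attenuated 34.2 Gy (34.2 + 19.8 = 54.0 Gy). At 1.8 Gy, 12 to 27 fit no stated dose.

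**6. Metastases, upper count of 13.** 36 + 13 × 1.8 = 59.4 Gy, an exact match. After 39.6 Gy it would be 63.0 Gy, which is 3.6 Gy above the stated maximum. After the attenuated 34.2 Gy it is 57.6 Gy, inside the range.

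**7. Section 5.2 against the table.** The upper ends for the primary site differ by 59.4 − 54 = 5.4 Gy if the pooled range is applied to that site alone. The 54 Gy limit in Section 5.2 for previously irradiated tissue agrees with the table.

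**The case against.** Most end-of-range counts are right once read as intended: both neuraxis counts, primary 10 after 36 Gy, primary 30 focally, and metastases 13 after 36 Gy. A clinician working to the total-dose column would not be misled. Section 5.9.2 also permits altered fraction sizes, a one-fraction reduction and attenuated totals, and Section 5.2 leaves several total doses to investigator discretion.

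Much of this stands, and it rules out three stronger readings a reader might draw.

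- **That the table as a whole fails to deliver its doses.** It does not: of the six end-of-range counts, only the metastasis 5 reaches no stated total.
- **That patients could be treated in compliance to 57.6, 63.0 or 45.0 Gy.** These figures pair a count with a craniospinal dose it does not fit. The documents prescribe none of those pairings.
- **That Section 5.2 flatly contradicts the table on the primary site.** Its range is pooled over primary and metastatic sites and varies with location, and the same section sets the 54 Gy limit. The pooled sentence is ambiguous for the primary site, no more.

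The permitted flexibility does not rescue the remaining defects. A one-fraction reduction from 6 may explain the 5, but it leaves 48.6 Gy. Fractions of 200 cGy leave 49.6 Gy. A lower craniospinal dose widens the shortfall. Discretion permits departures from the table; it does not make the two columns agree.

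**Conclusion.** The point holds in a limited form. One count, the metastasis minimum of 5, cannot reach its stated minimum after any stated craniospinal dose: it falls short by 1.8 Gy after 39.6 Gy and by 5.4 Gy after 36 Gy. One range, primary 10 to 30, omits every count that fits after 39.6 Gy and two that fit after 36 Gy, and spans counts that fit neither a boost after 36 to 39.6 Gy nor a focal course. The metastasis maximum of 13 matches after 36 Gy but overshoots after 39.6 Gy. Underlying all of this, the table mixes cumulative doses with boost counts and does not say so.

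This rests on reading the smaller counts as boosts, which Sections 5.7.2 and 5.9.5 support, and on the table's 180 cGy per fraction except where another size was tested. It does not show that anyone was wrongly dosed. It should be corrected because it sits in the prescription for the trial intervention and affects compliance checks.

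**What to change.** The protocol team, led by radiation oncology, should:

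1. reconcile the total-dose and fraction columns in Section 5.9.2;
2. state which doses are cumulative and which counts are boost fractions, listing boost counts separately for each craniospinal dose, including the permitted attenuated doses, and separately for focal treatment alone;
3. say whether the 30-fraction sentence below the table applies only to focal treatment;
4. reword the pooled range in Section 5.2 so that it can be read alongside the table and the limit for previously irradiated tissue.

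The doses are for the team to decide; none is proposed here. The cost is a correction to one table and a sentence or two of text, with no change to the statistical design.
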